### 3.9.2.3 Variables for CBCT acquisition

-the linear deviation of the tip and cap of the TADs in the mesio-distal, buccal-lingual, and vertical three-dimensional directions

-the angle deviation of the head and tail of the TADs in the mesio-distal, buccal-lingual, and vertical three-dimensional directions

-the distance between TADs and tooth root and maxillary sinus, and the distance between two tooth roots.

-The thickness of the inner and outer walls of the maxillary sinus

-the root resorption

-the thickness of the lingual bone of the TADs

-the thickness of the cancellous bone.

### 3.9.2.4 Independent variables

Gender

Age

## 3.10 Data collection and grouping

Twenty four (24) individuals who met the criteria will be randomly divided into 2 groups, 12 will be selected as the experimental group and mini-implants will be

implanted using guide plates, while others 12 participants will be selected as the control group and implanted mini-implants based on experience and no guide plates.

**The recruitment will take about two months, using hospital bulletin boards and social media at Beijing Xuanwu TCM Hospital. All routine orthodontic diagnostic records will be collected. The patient was asked to sign an informed consent form before surgery, which took about 20 to 30 minutes. The doctor implanted the miniscrew, and the operation time was about half an hour. The study design will be used as assigning intervention and control group randomly. The postoperative clinical and imaging evaluation was about 6 months.**

### **3.11 Stages of treatment**

- 1) The patient undergoes routine pre-orthodontic examination, model analysis, cephalometric measurement, and develops an orthodontic treatment plan.
- 2) .The patient undergoes routine pre-orthodontic examination, model analysis, cephalometric measurement, and develops an orthodontic treatment plan.
- 3) The process of insertion of miniscrew will be depend on the group either **Intervention** Group or **Control** Group. The guide plate will be used for miniscrew insertion in **Intervention** Group and experience based on the patient's digital films for **Control** Group. The area of insertion of the miniscrew will be the upper alveolar ridge between premolars and molar tooth. The procedure will be performed under local injection anesthesia.
- 4) The process of implanting implant nails on **Intervention** Group is as follows: the material and model of the implanted micro implant nails are exactly the same as those of the traditional positioning set. The implant nail diameter is 2mm and the length is 10 mm. The implant surgery was performed by the same orthodontist in accordance with recommended operating procedures. Preoperative local anesthesia will be performed, and micro-implant nails will be implanted at the intended

implantation site under the guidance of the guide plate. The area of implantation is maxillary zygomatic alveolar ridge.

**5) The process of implanting implant nails on the Control Group is as follows:**

**Similar to the intervention group, but the doctor implant the miniscrew based on experience with CBCT scans.**

6) Collect date before and after implant nail implantation. The digital plaster models will be obtained by scanning with a D700 scanner (3shape, Denmark). Both digital models and CBCT scan data will be imported into Segma implant guide software (Beijing, China). The combination method is as follows: first, open the file in a way that only uses CBCT for implant design and adjust the density of anatomical landmarks such as the maxillary sinus, condylar foramen, or protrusions to an explicit level. Then, the teeth or jaw landmark points of the model and CBCT will be selected to reconstruct a 3D model.

4) The data collection will be performed by obtaining plaster model using intraoral scanner at T1(immediate post insertion) and T2 (6 months post insertion)

### **3.12Design and fabrication of guide**

The proposed structure will be made of three main components: a tooth guide part, a gingival guide part, and a steering part. The tooth guide and gingival guide parts are firmly connected by fracture lines. The mini-implant guide part is specifically designed to accommodate the angle and position required for miniscrew insertion. On the basis of the resin guide plate, add a guide hole structure and change it to a three-quarters circular shape.

During usage, the guide can be pre-designed in accordance with the desired planting

position and direction of the patient's mini-implant, enabling precise guidance during the implantation process. The designed guide's data is inputted into EnvisionTEC Vida 3D printer to create the mini-implant guide. Prior to the implantation of the mini-screw, patients will be informed about the potential risks and required to sign an informed consent form. The implantation procedure using the guide involved the insertion of a 2mm diameter and 13mm length mini-implant (Cibei, Ningbo, China) (Fig6) into the patient's maxillary zygomatic alveolar ridge. Upon completion of implantation, the guide will be removed.

Figure 3.12 A guide with a three-quarters circular hole

### 3.13 Analyses and measurements:

#### 1. Main efficacy indicators.

A. CBCT analysis indicators: Based on the ideal position of the implant designed before surgery as the standard, the researcher will measure the linear deviation of the tip and cap of the TADs in the mesio-distal, buccal-lingual, and vertical three-dimensional directions, the angle deviation of the tip and cap of the TADs in the mesio-distal, buccal-lingual, and vertical three-dimensional directions, the distance between TADs and tooth root and maxillary sinus, and the distance between two tooth roots.

B. Clinical data analysis: The mobility of TADs. : The stability of a miniscrew can be evaluated through clinical examination by checking for mobility, and implant loosening and displacement.

## 2. Secondary efficacy indicators:

A. CBCT analysis indexes: The thickness of the inner and outer walls of the maxillary sinus, the root resorption, the thickness of the lingual bone of the TADs, the thickness of the cancellous bone, the position of the miniscrew, the surrounding bone density, and any signs of bone loss or inflammation around the screw.

B. Clinical data indicators: Implant diameter, length, gingival type, gingival color and texture, plaque index, depth of exploration, bleeding index, and symptoms.

Complications will be defined as obvious symptoms, swollen gums, mucous membranes, clinical mobility of TADs, root resorption, or obvious changes in normal anatomy around TADs, such as maxillary sinusitis.

[figure not shown]
[figure not shown]

Figure3.13 digital 3D model

**3.Accuracy of miniscrews : -the linear deviation of the tip and cap of the TADs in the mesio-distal, buccal-lingual, and vertical three-dimensional directions**

**-the angle deviation of the head and tail of the TADs in the mesio-distal, buccal-lingual, and vertical three-dimensional directions**

**-the distance between TADs and tooth root and maxillary sinus, and the distance between two tooth roots.**

**-the thickness of cortical bone and cancellous bone**

**4.Stability of miniscrews : -Looseness of mini-implant**

**5.Safety of miniscrews : Distant of the root to the miniscrew tip**

**Distant between miniscrew tip to the maxillary sinus**

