#### **Specific Objective**

The specific objectives for this study will be:

1. To compare the accuracy of miniscrews implanted using modified template by computer-aided design and without template guide (conventional method).

2. To compare the stability of miniscrews implanted using modified template by computer-aided design and without template guide (conventional method).
3. To compare the safety of miniscrews implanted using modified template by computer-aided design and without template guide (conventional method).
4. To compare the accuracy of miniscrew implantation between using CBCT and digital model investigating.

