#### **1.11.4 Alternative hypotheses**

1. There is a significant difference in the accuracy of miniscrews implanted with and without guide.
2. There is a significant difference in the stability of miniscrews implanted with and without guide.

3. There is a significant difference in the safety of miniscrews implanted with and without guide.
4. There is a significant difference in the accuracy of miniscrew implantation between using CBCT and digital model investigating.

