**-the distance between TADs and tooth root and maxillary sinus, and the distance between two tooth roots.**

**-the root resorption**

### 3.14Statistical analysis

Two doctors with more than 2 years of clinical CBCT image analysis experience performed image superimposition and measurement: everyone measured images once, with a 1-day interval, for a total of 3 measurements, and the average value was

taken. The linear deviation of the mini-implant tip and cap and the angular deviation of the long axis of the mini-implant in the bucco-palatal, mesio-distal and vertical directions were measured. The results were analysed by the SPSS statistical package version 19.0 (Chicago, USA). The Kruskal-Wallis H test of the multiple independent samples method was used to compare the three groups of mini-implant' deviation in the three directions. For the values that did not conform to a normal distribution, the Bonferroni method was used to correct the significance level for pairwise comparisons. One-way ANOVA was used for values that conformed to a normal distribution. P value less than 0.05 will be considered significant.

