#### **the distance between miniscrew and the tooth root**

Intervention / Control groups		
Distance x axis	Distance Y axis	Distance Z axis

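### Safety (objective 3) is defined by root and sinus distances plus root resorption; most complications the protocol itself defines, and site infection, fall outside it

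*Protocol*

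**What the plan says.** Objective 3 (Specific Objective, section 1.11.2) is "To compare the safety of miniscrews implanted using modified template by computer-aided design and without template guide (conventional method"), and hypothesis 3 (section 1.11.4) is "There is a significant difference in the safety of miniscrews implanted with and without guide".

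Section 3.13, item 5, defines the outcome. It begins "Safety of miniscrews : Distant of the root to the miniscrew tip", continues with "Distant between miniscrew tip to the maxillary sinus" and "the distance between TADs and tooth root and maxillary sinus, and the distance between two tooth roots", and ends with "the root resorption".

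Section 3.13, item 2, headed as secondary efficacy, contains the definition of harm: "Complications will be defined as obvious symptoms, swollen gums, mucous membranes, clinical mobility of TADs, root resorption", followed by marked anatomical change around the screw, with maxillary sinusitis as the example. Nothing in the protocol connects this definition to objective 3 or hypothesis 3.

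Three other places bear on the point:
- Section 3.5.3 sizes objective 3 on a mean difference of 0.66 with a standard deviation of 0.12 mm.
- Annexure B (section 4.2), the dummy table for safety, holds one item, "the distance between miniscrew and the tooth root", on three axes.
- Section 3.18 foresees infection, loosening or loss of the screw, and root injury. Section 3.7.3 makes infection, unmanageable pain, bone resorption and loosening grounds for withdrawal.

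**The concern.** Distance from the root or sinus indicates the risk of harm; it is not harm itself. The protocol argues for the guide partly on fewer complications and a safer procedure (sections 1.9, 1.10 and 3.19), yet the outcome that answers the safety question leaves out most of the complications it defines.

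The distances also do double duty. The screw-to-root, screw-to-sinus and inter-root distances appear among the main efficacy indicators (3.13 item 1A), under accuracy (item 3) and under safety (item 5). A guide that places screws more accurately would therefore tend to look safer on much the same measurements. Symptoms, swelling, sinusitis or infection could be more frequent in one arm without entering the answer to objective 3.

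**Working it through.** **1. Where each harm is placed.** The first five rows are the components of the definition in 3.13 item 2.

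| Harm | In safety (3.13 item 5)? | Where else |
|---|---|---|
| Obvious symptoms | No | Item 2B |
| Gum or mucosal swelling | No | Item 2; related gingival signs in 2B and 3.9.2.1 |
| Screw mobility | No | Stability: items 1B and 4 |
| Root resorption | Yes | Items 2A and 3.9.2.3 |
| Anatomical change, e.g. sinusitis | No | Item 2 only |
| Site infection | No | 3.7.3 and 3.18 only |

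One of the five components is in safety, one is handled as stability, and three are in neither.

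**2. The planned size for objective 3.** Inputs from 3.5.3: effect size 1.3929508, type I error 0.05 (two-sided assumed), power 0.8. For a two-sample t-test the noncentrality is d√(n/2).
- With n = 10 per group: 1.3929508 × √5 = 3.11 on 18 degrees of freedom, power 83.8%. Ten is the smallest n reaching 80%, so the stated figure is reproduced.
- With n = 12 per group: 1.3929508 × √6 = 3.41 on 22 degrees of freedom, power 90.3%.

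(The stated 0.66 and 0.12 give 0.66/0.12 = 5.5, not 1.39. That is a separate inconsistency and does not affect this point.) The calculation confirms that objective 3 was conceived as a comparison of a millimetre measure.

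**3. What 12 per arm can say about complications.** The protocol gives no complication rate, so all rates here are assumptions.

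| Assumed rates | Fisher exact power, 12 per arm | Same, 10 per arm | n per arm for 80% (pooled formula) |
|---|---|---|---|
| 10% v 30% | 9.5% | 5.7% | 62 |
| 10% v 40% | 23.3% | 15.2% | 32 |
| 10% v 50% | 42.5% | 29.5% | 20 |

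The first pooled result is [1.96√(2 × 0.2 × 0.8) + 0.8416√(0.1 × 0.9 + 0.3 × 0.7)]² / 0.2² = 1.570² / 0.04 ≈ 61.6, rounded up to 62. Against 0 of 12, at least 5 events in the other arm are needed for significance. For 0 of 12 the exact two-sided 95% upper limit is 1 − 0.025^(1/12) = 26.5%.

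**4. How often distances and complications could disagree.** Assume the two are independent, that the distance effect is as planned, and 12 per arm. The chance that distance significantly favours the guide while the guided arm has more observed complications is the product of the two probabilities:
- 30% guided v 10% control: 0.903 × 0.845 = 76%
- 20% v 10%: 0.903 × 0.657 = 59%
- 10% v 10%: 0.903 × 0.359 = 32%

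The last line shows that such disagreement is common even when the true rates are equal.

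**The case against.** The omission is partial. Root resorption is a biological harm and is in the safety list; mobility is compared under stability. Symptoms, gingival state, bleeding index and CBCT signs of inflammation are all listed in 3.13 item 2, and nothing prevents their being reported by arm. Detailed complication tables are commonly left to an analysis plan or case report form. All of this is fair, and it limits the point to how item 5 defines safety. It does not remove it, because the protocol itself defines the outcome for objective 3 and puts its definition of complications elsewhere.

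Four stronger readings are tempting, and the protocol does not support them:
- *Safety is judged on geometry alone.* Root resorption in item 5 contradicts this.
- *The three axes in Annexure B are tested separately, so a closer screw could rank as safer.* No section says so. The direction-wise tests in 3.14 concern placement deviation. If the three values are components to one root reference point, the full distance can be recovered.
- *Only root distance is recorded.* Annexure B is a dummy table; 3.9.2.2, 3.9.2.3 and 3.13 also list sinus distance and root resorption.
- *The plan lets the guide be declared safer despite more complications.* That is a possible consequence, not a written rule. Hypothesis 3 is non-directional.

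**Conclusion.** The point holds as a fault in how the outcome is defined. Followed as written, the answer to objective 3 rests mainly on proximity measures, most of which are also accuracy outcomes. Three of the five defined complication components are in neither safety nor stability, and site infection is in no outcome list. This rests on the text and on no assumed rate.

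The probabilities in the working are illustrations only. They depend on assumed rates, independence and the planned effect size, and do not estimate what this trial will show. The correction does not give the trial power for complications: at 12 per arm they can be described but not usefully tested. It is a cheap improvement worth making before data are analysed, and it does not invalidate the distance comparison.

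**What to change.** In section 3.13, item 5, add: *the number of participants in each arm with at least one complication as defined in item 2, or infection at the screw site, up to 6 months, counted in all randomised participants including those withdrawn under 3.7.3.* Infection must be named because item 2 does not name it. Withdrawn participants must be included because several grounds for withdrawal are themselves complications.

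Report the counts descriptively, with exact confidence intervals, beside the distances. Show mobility separately as well, since it is the stability outcome. Call the distances proximity (surrogate) measures, and word any safety conclusion to cover both kinds of evidence.

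Do not make the conclusion depend on which arm has the higher complication count. At an assumed 10% in both arms the guided arm would have more events by chance about 36% of the time.

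In Annexure B, add fields for complications, tip-to-sinus distance, root resorption and the shortest three-dimensional screw-to-root distance.

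Cost: one paragraph and a few form fields. Most of the underlying signs are already listed for collection, but complications and infection need their own entry. The downside is a more modest safety claim.

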### **3.5.3 Objective3**

Sample size calculation based on the objective 1 related to the of guide on the miniscrew implantation. In a previous study the response within each subject group was normally distributed with standard deviation 0.12mm(Janson G, et al.,2013). If the true difference in the experimental and control means is 0.66, the research will need to study 10 experimental subjects and 10 control subjects to be able to reject the null hypothesis that the population means of the experimental and control groups are equal with probability (power) 0.8. The Type I error probability associated with this test of this null hypothesis is 0.05. The effective size is 1.3929508.

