### 3.9 Variables and tools

#### 3.9.1 Research tool

3.9.1.1 Routine orthodontics records before treatment

History and examination record

Digital model

CBCT

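### Objective 3 is sized, and the named tests run, without adjusting for each patient's anatomy, although pre-treatment CBCT could supply one covariate per safety distance

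*Protocol*

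**What the plan says.** **Sizing.** Section 3.5.3 plans objective 3 (safety) as a comparison of two means: "If the true difference in the experimental and control means is 0.66", with the response "normally distributed with standard deviation 0.12mm". It adds "The effective size is 1.3929508" and concludes that the trial will "need to study 10 experimental subjects and 10 control subjects" to reject equal means "with probability (power) 0.8". No covariate enters. The section does not say whether the figures refer to the root or the sinus distance. Its 10 per arm is the largest of the four objectives (8, 8, 10 and 6), so it drives the total of 24.

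**Endpoints.** Section 3.13 item 5 lists root-to-tip distance and "Distant between miniscrew tip to the maxillary sinus" as safety measures. Section 3.9.2.3 lists "the distance between TADs and tooth root and maxillary sinus, and the distance between two tooth roots" among the CBCT variables. Inter-root distance therefore appears as something measured, but nowhere as a baseline variable.

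**Tests.** Section 3.14 names Kruskal-Wallis for the deviations, in three groups although the trial has two, and one-way ANOVA for normally distributed values. Neither carries a covariate, and the safety distances are not mentioned. The independent variables in section 3.9.2.4 are gender and age. The matching examples in section 3.6 include no anatomical measure.

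**What exists before placement.** CBCT stands under "Routine orthodontics records before treatment" (section 3.9.1.1). Section 3.11 has the control arm implanted with reference to CBCT scans. Section 3.13 item 1A measures deviation from an ideal position designed before surgery.

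**The concern.** How far a screw tip ends up from a root or from the sinus depends on where the operator puts it and on how much room the patient has. The first is the effect under study. The second varies between patients, is fixed before treatment, and can be seen on a scan that is already taken. If it is left out, it inflates the residual variance. With 12 per arm and simple randomisation, a chance imbalance in anatomy also goes uncorrected. A real gain in clearance from the guide could then be estimated less precisely than the collected data allow.

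**Working it through.** **Inputs.** From section 3.5.3: difference 0.66, SD 0.12 mm, effect size d = 1.3929508, 10 per arm, power 0.80, alpha 0.05. Two-sided testing is assumed, because the hypotheses are non-directional. From section 3.5.4: total 24 after 20% drop-out. The correlation r between pre-treatment space and achieved clearance is not in the documents; r = 0.3 to 0.7 is assumed, with lower values shown for the downside.

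**Step 1: reproduce the plan's figure.** For a two-sample t test the noncentrality is d × √(n/2) = 1.3929508 × √5 = 3.115 on 18 df. Power is 0.838 at 10 per arm and 0.792 at 9, so the stated 10 follows from d = 1.393. It does not follow from the printed difference and SD: 0.66/0.12 = 5.5, which would need only 3 per arm by the t test. An effect size of 1.393 with a difference of 0.66 implies an SD of 0.66/1.3929508 = 0.474. For drop-out, 20 × 1.2 = 24 matches the stated total.

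**Step 2: add one baseline covariate.** ANCOVA multiplies the residual variance by (1 − r²), uses 2n − 3 = 17 df, and pays a factor 1 + 1/(2n − 4) = 1 + 1/16 = 1.0625 for estimating the slope. The SE ratio to the unadjusted analysis is √[(1 − r²) × 1.0625]. The CI ratio also carries the change in t quantile, 2.1098/2.1009 = 1.0042.

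| r (assumed) | 1 − r² | SE ratio | CI change | Power at 10 per arm |
|---|---|---|---|---|
| unadjusted | – | 1 | – | 0.838 |
| 0 | 1.00 | 1.031 | 3.5% wider | 0.813 |
| 0.2 | 0.96 | 1.010 | 1.4% wider | 0.828 |
| 0.3 | 0.91 | 0.983 | 1.3% narrower | 0.847 |
| 0.5 | 0.75 | 0.893 | 10.4% narrower | 0.908 |
| 0.7 | 0.51 | 0.736 | 26.1% narrower | 0.978 |

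On the variance scale, r = 0.5 and r = 0.7 are worth 1/(0.75 × 1.0625) − 1 = 25% and 1/(0.51 × 1.0625) − 1 = 85% more patients.

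**Step 3: break-even.** The SE is unchanged when (1 − r²) × 1.0625 = 1, so r² = 1/17 and r is about 0.24.

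**Step 4: a smaller effect.** If d were 1.0 (an assumption; the documents do not use it), power at 10 per arm would go from 0.562 unadjusted to 0.573, 0.656 and 0.817 at r = 0.3, 0.5 and 0.7.

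**The case against.** **A covariate belongs in the SAP, and an unadjusted randomised comparison is valid.** Both statements are true. An SAP that is not shown may name a covariate, and nothing here biases the result. The point stands as one of method: the protocol does state its sizing and its tests, both are unadjusted, and a better analysis is available at small cost.

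**The safety test is not fixed.** A reader might infer that the protocol prescribes a comparison of raw arm means for both distances. It does not: section 3.14 names no test for either, Kruskal-Wallis compares ranks, and section 3.5.3 does not say which distance was sized. What can be said is that the sizing and every named test are unadjusted.

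**The gain is not free.** This stands. It rests on a correlation the documents do not give, costs one degree of freedom, and turns into a small loss below r of about 0.24.

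**Inter-root width may not be the relevant space.** A reader might infer that inter-root width caps the clearance geometrically. That assumes a shaft lying between two roots. Section 3.11 step 3 names the ridge between premolars and molar, while step 4 and section 3.12 name the zygomatic alveolar ridge; section 3.13 item 5 measures from the tip. Screw length is 10 mm in section 3.11 and 13 mm in section 3.12, which bears on any tip distance. No such bound is supported, and the covariate must fit the actual site and endpoint.

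**At the printed SD adjustment could not matter.** With d = 5.5 power is already near 1. This is a consequence of the contradiction inside section 3.5.3; the sample size itself rests on d = 1.393.

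**Timing and pairing.** The protocol does not say that planning precedes allocation. If it follows, the chosen site could depend on arm, and blinding the reader of the scan would not cure that. The pairing described in section 3.6 is a separate conflict with simple randomisation, which ANCOVA does not resolve.

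**Conclusion.** The point holds as a missed opportunity for precision and is no threat to validity. The protocol's sizing and named tests ignore each patient's available space, although pre-treatment CBCT and a pre-surgical planned position can supply it. The benefit ranges from about one point of power at r = 0.3 (0.838 to 0.847) to 14 points at r = 0.7 (0.978), with intervals about 1% to 26% narrower. The worst case is power 0.813 at r = 0. These figures assume 10 evaluable per arm, d = 1.393, two-sided 0.05 and an approximately normal linear model, and r is an assumption throughout. They do not justify a smaller trial. Three conflicts affect what the covariate should be and how large the planned effect is: the insertion sites, the screw lengths, and 0.66 with 0.12 against 1.393.

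**What to change.** Keep the sample size. State in sections 3.13 and 3.14:

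- **Model:** one ANCOVA for each safety distance (tip to root, tip to sinus), with arm plus one matching pre-treatment CBCT covariate.
- **Covariate:** either the same distance at the pre-surgically planned position or the available space at the actual insertion site. Choose one in advance for each endpoint and apply it to both arms.
- **Timing:** fix the site and read the covariate before allocation.
- **Reporting:** the adjusted difference with its 95% CI, and the unadjusted result in support.

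Before this can be made exact, the passages on insertion site (section 3.11 steps 3 and 4, section 3.12), on screw length (sections 3.11 and 3.12) and on the planning figures (section 3.5.3) must be reconciled, and section 3.5.3 should name the distance it sizes.

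The cost is two readings per participant on scans already taken, one degree of freedom per model, a few lines of text, and a small loss of power if r is below about 0.24. No extra patients or imaging are needed.
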